NCT02403817 Training Attention and Eye Movement in ASD 8/8/2019

Study Protocol and Statistical Plan

Current therapies for Autism Spectrum Disorder (ASD) target social and language behaviors, but due to the highlevel nature of these skills any improvement rarely extends beyond the targeted behavior. This project uses new technology to implement a novel concept for behavioral intervention to improve basic attention and eye movement skills in ASD. Children will play gaze-driven video games at home during the intervention, receive pre- and post-training assessment of attention, and eye movement function. Because these basic skills form the foundation for good social communication, training these abilities has the potential to improve a broad spectrum of clinical symptoms, and in young children may affect the course of development.

This is a pilot project with a small clinical trial. The aims are:

1: Conduct video game training system with 2 groups of 20 ASD children/teens/young adults (aged 9-26).

2: Evaluate efficacy of training using 3 levels of outcome measures for pre- and post- testing and followup. Level 1 will be a direct test of attention and eye movement. Level 2 will test attention and eye movement function in a digital environment. Level 3 will test the effect of training on social skills measured by questionnaires and in a live social interaction.

Research Design and Methods

We will recruit 40 male and female children with ASD (ages 9-26) to participate in the clinical trial. Participants will meet the criteria for Inclusion and Exclusion described below (we have an existing pool of potential participants that meet inclusion criteria, but expect to screen 50 children to find 40 that meet study criteria).

Collaborator [name] (Rady Children's Hospital) will be responsible for diagnosis of participants who do not already have required diagnostic assessment. [name] is the Clinical Director Rady Children's Hospital Autism Discovery Institute (ADI). [name] is ADI-R and ADOS reliable and is a certified trainer for both instruments. ASD participants will be recruited by [name] through ADI. We also have a large pool of children and teens with ASD from previous studies who meet diagnostic standards, the majority of whom will be willing to participate in the proposed project.

General inclusion/Exclusion criteria:

- 1. All participants must be cooperative and able to follow instructions.

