Social Interaction Task: The third level of outcome assessment will test change in social behavior measured by questionnaires (SRS) and a live social situation between the research participant and a tester. Trainees will be engaged in an interactive conversation in which the tester uses a scripted conversation or games and set of cues to direct attention and eye movement. The script will involve several explicit and implicit redirections of attention and eye movement during the conversation between participants, using props in some cases to guide attention and gaze. Eye movements during the interaction will be measured with a lightweight eye-tracker worn by both participant and tester (based on a tracker from Pupil Labs with our modified hardware and software). The entire interaction will also be videotaped for off-line coding and scoring of language and validation of automatic measures of eye contact.

Analysis: Standard analyses will compare number and timing of instances of orienting to or disengaging from a directed social stimulus (repeated measures ANOVA comparing pre- and post-training measures and groups and interactions). More advanced analysis will use methods developed by [name]. Linguistic and Nonverbal communicative behaviors will be annotated into the Eudico Linguistic Annotator (ELAN) (Brugman, H., & Russel, A., 2004; Crasborn, O., & Sloetjes, H., 2008). ELAN, a video interface integrates behavioral data at millisecond resolution across multiple channels such as speech, eye gaze, head movement and facial expression. Behavioral states and discreet behaviors can be coded yielding frequency counts, total duration and mean duration as well as the coordination across channels, e.g., integrating an eye gaze shift in response to a question. These analyses include following behavioral categories: (i) Gaze: Location (target), Duration, Frequency; (ii) Head: position and movement; (iii) Speech (transcribed using CHILDES): utterances (content and length) and pauses.

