From these analyses, it is possible to determine the degree to which participants respond appropriately, both linguistically and behaviorally to social interactive cues. We will examine both speech and non-verbal indications of engagement, such as gaze and gestures. This high level outcome measure allows us to examine the subtleties of social engagement during a conversation. We expect that post-intervention improved attention and eye movement will promote more effective social interaction.

Statistical Plan

All outcome testing will be done before training then repeated after training completion.

Level 1 (and Screening for entry criteria): The first level will use tests we have developed and published to directly test whether the speed, accuracy, and spatial breadth of eye movements and attention have improved. These tasks will be used to screen participants for presence of attention and eye movement deficits and will be used as a direct test of improvement of spatial attention disengagement and shifting and eye movement accuracy and initiation speed.

Measures to be analyzed (indices of attention orienting and disengagement, saccade accuracy, latency and gaze/attention) disengagement are described above as are analyses to evaluate effects at the single case level. Analyses will evaluate treatment outcome and differences in outcome between the two groups. A multivariate analysis (MANOVA) will provide a global (linear vector) comparison of all outcome measures at preand post-testing points for the two groups (i.e., differences in all measures between pre- and post-testing and between groups). Repeated measures ANOVAs for each of the five outcome measures will test improvement over time (slope > 0) and trends (linear, non-linear), and differences between groups in these effects. Level 2: The second level will use a driving simulation to test how well the trainee can negotiate a simulated environment with a variety of obstacles (i.e., test improvement in attentional and visual monitoring and speed and accuracy of response).

Simple analyses will compare (repeated measures ANOVA to examine differences in pre- and post-measures and group differences and interactions).

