Level 3: The third level will test change in social behavior measured by questionnaires and a live social situation between the research participant and two testers. Trainees will be engaged in a three-way interactive conversation in which the testers use a scripted conversation and set of cues to direct attention and eye movement, videotaped for off-line coding and scoring. The script will involve several explicit and implicit redirections of attention and eye movement during the conversation between participants, using props in some cases to guide attention and gaze. We will work with our colleague and consultant on this project, [name], an expert in designing and analyzing this sort of interaction. [name] will ensure that the script and design are appropriate, the cameras are placed optimally for capturing the participants and that our plan for transcribing the interaction is sound and will reveal subtleties of social attention redirection. [name] will develop the coding system and will train students to score the videotapes.

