Standard analyses will compare number and timing of instances of orienting to or disengaging from a directed social stimulus (repeated measures ANOVA comparing pre- and post-training measures and groups and interactions). More advance analysis will use methods developed by [name]. Linguistic and Nonverbal communicative behaviors will be annotated into the Eudico Linguistic Annotator (ELAN) (Brugman, H., & Russel, A., 2004; Crasborn, O., & Sloetjes, H., 2008). ELAN, a video interface integrates behavioral data at millisecond resolution across multiple channels such as speech, eye gaze, head movement and facial expression. Behavioral states and discreet behaviors can be coded vielding frequency counts, total duration and mean duration as well as the coordination across channels, e.g., integrating an eye gaze shift in response to a question. Drs. [name] and [name] have developed methods for coding social behaviors in typical and atypical children and adults. These analyses include following behavioral categories: (i) Gaze: Location (target), Duration, Frequency; (ii) Head: position and movement; (iii) Speech (transcribed using CHILDES): utterances (content and length) and pauses. From these analyses, it is possible to determine the degree to which participants respond appropriately, both linguistically and behaviorally to social interactive cues. Novel analyses developed by [name] (a consultant on this project) use a recurrence technique in which the level of engagement of the participants is revealed in the pattern of their exchange (Figure 4). We will examine both speech and non-verbal indications of engagement, such as gaze and gestures. We will also obtain SRS scores to compare aspects of social engagement with a standardized assessment. This high level outcome measure allows us to examine the subtleties of visual and spoken engagement during a conversation. We expect that our intervention would promote more effective social interaction.

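### Level 3 timing is defined only for cues that were answered and mixes explicit with implicit cues, so it can be biased towards slower when responding improves

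*Combined protocol and SAP*

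**What the plan says.** The standard Level 3 analysis appears twice in the combined protocol and SAP, in the Analysis paragraph under Social Interaction Task and under Level 3 of the Statistical Plan: "Standard analyses will compare number and timing of instances of orienting to or disengaging from a directed social stimulus". The method is given as "repeated measures ANOVA comparing pre- and post-training measures and groups and interactions".

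Both sections describe the stimulus in the same way: "The script will involve several explicit and implicit redirections of attention and eye movement during the conversation between participants". The number of redirections is not stated. Under Social Interaction Task, "the tester uses a scripted conversation or games and set of cues to direct attention and eye movement". Level 3 of the Statistical Plan instead describes a three-way conversation with two testers.

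The video annotation adds "frequency counts, total duration and mean duration as well as the coordination across channels". None of these is stated per cue delivered. Both accounts name the appropriateness of responses to social cues as an aim, but do not turn it into a measure. The documents give no rule for a cue that draws no response and no analysis by cue type.

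**The concern.** Timing exists only where a response occurred, and responding is what training is meant to change. The set of cues behind the timing mean can therefore differ between visits and between groups. If a trained participant begins to answer implicit cues that were previously missed, and these take longer to answer, the slow responses enter the post-training mean with no counterpart before training. The mean can rise although no type of cue is answered more slowly.

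The count has a separate weakness. Without a fixed number of cues or a denominator, it depends on opportunities as well as behaviour.

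Level 3 is where the trial looks for benefit beyond the trained skills. A timing result that understates a gain, or has the wrong sign, would be hard to interpret. The plan does not say how number and timing are to be read together when they disagree.

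**Working it through.** The documents give no response rates, latencies, number of cues or effect size for Level 3, so there is no planned figure to reproduce. Every input below except 20 per group is an assumption, and the results show direction and range only.

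**1. Expected mean timing of answered cues**

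Assume 6 explicit and 6 implicit cues. Response rates are 80% and 30% before training, 85% and 60% after.

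- Expected responses before: 6×0.80 + 6×0.30 = 4.8 + 1.8 = 6.6.
- Expected responses after: 6×0.85 + 6×0.60 = 5.1 + 3.6 = 8.7.
- Mean timing = (explicit responses × explicit latency + implicit responses × implicit latency) / all responses.

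With latencies of 600 and 1200 ms:

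- Before: (4.8×600 + 1.8×1200)/6.6 = 5040/6.6 = 763.6 ms.
- After, no change in speed: (5.1×600 + 3.6×1200)/8.7 = 7380/8.7 = 848.3 ms.
- After, both types 5% faster: (5.1×570 + 3.6×1140)/8.7 = 7011/8.7 = 805.9 ms.
- After, both types 10% faster: (5.1×540 + 3.6×1080)/8.7 = 6642/8.7 = 763.4 ms.

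| Explicit / implicit latency before (ms) | True speed gain | Mean before | Mean after | Reads as |
|---|---|---|---|---|
| 600 / 1200 | 0% | 763.6 | 848.3 | slower |
| 600 / 1200 | 5% | 763.6 | 805.9 | slower by 42 |
| 600 / 1200 | 10% | 763.6 | 763.4 | no change |
| 600 / 800 | 0% | 654.5 | 682.8 | slower |
| 600 / 800 | 5% | 654.5 | 648.6 | faster by 6 |
| 600 / 600 | 5% | 600.0 | 570.0 | faster by 30 |

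The artefact is the change in the implicit share of responses times the latency gap. The share goes from 1.8/6.6 = 0.273 to 3.6/8.7 = 0.414, a rise of 0.141. That adds about 85 ms at a 600 ms gap, 28 ms at 200 ms and nothing at no gap. In the 200 ms case the sign is right, but true gains of 30 ms (explicit) and 40 ms (implicit) show as 6 ms.

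**2. Simulation at 20 per group**

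This used different assumed inputs: explicit response rate 0.8 throughout; implicit rate 0.2, rising to 0.6 in the trained group only; explicit latency 800 ms; within-participant SD 250 ms and between-participant SD 120 ms; 1,000 trials per setting. The test was a t-test on change at two-sided 5%, which equals the group-by-visit test with two visits. The timing test was significant in the wrong direction in these percentages of trials:

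| True speed gain | Gap 200 ms | Gap 400 ms | Gap 600 ms |
|---|---|---|---|
| 0% | 19% | 47% | 68% |
| 5% | 3% | 13% | 33% |
| 10% | 0.1% | 3% | 11% |
| 20% | 0% | 0% | 0% |

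With the number of cues fixed, the count test showed benefit in 94–96% of trials.

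**3. Count when the number of cues differs**

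Let the response rate rise from 0.5 to 0.6. If cues fall from 12 to 10, the count goes from 6.0 to 6.0. If they fall from 12 to 9, it goes from 6.0 to 5.4.

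**4. Keeping non-responses in**

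Take the 600 ms gap with a 5% gain, and hold each non-response at an assumed 3000 ms window.

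- Before: (5040 + 5.4×3000)/12 = 21240/12 = 1770 ms.
- After: (7011 + 3.3×3000)/12 = 16911/12 = 1409 ms.

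The direction is right. With no speed change the second figure would be (7380 + 9900)/12 = 1440 ms, so 330 of the 361 ms reflects more responding and 31 ms reflects speed. The measure combines the two and depends on the window, so it should be shown by cue type beside the proportion followed. In the simulation it was significant in favour of training in 85–99% of trials and in the wrong direction in about 0%.

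**The case against.** The strongest reply is that the reversal depends on chosen inputs. The documents never say that implicit cues are answered more slowly, and a modest speed gain or a smaller gap removes the reversal. That stands. What remains is a bias towards slower, whose size is unknown, whenever there is a gap and responding to implicit cues rises.

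The plan also compares number as well as timing. In the illustration the number rises from 6.6 to 8.7, so a reader would see a mixed result and not plain worsening. The social questionnaire and the recurrence analysis are reported as well. This limits the damage but does not correct the timing comparison.

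A script with a set of cues, together with the statement "All outcome testing will be done before training then repeated after training completion", may well mean the same cues at both visits. Counts and proportions would then be equivalent. The allowance for games and the differing descriptions of the interaction leave this open, so it needs a clarification.

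The joystick group plays the same games. If its members also come to answer more implicit cues, part of the artefact cancels in the group contrast. The simulation let only the trained group improve.

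Finally, a consultant is to develop the coding system, and one coding example links a gaze shift to a question. Per-cue scoring may be intended, but the stated analysis does not use it.

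Two stronger readings are not supported:

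- **The most impaired participants drop out for want of a timing value.** That needs no response at all at a visit. At the illustrated pre-training rates the chance is 0.2^6 × 0.7^6, about 8 in a million. It reaches 0.9^12 = 28% only for someone who answers 10% of 12 independent cues (0.8^12 = 7% at 20%), and nothing shows that such participants are expected.
- **Orienting and disengaging are summed.** The text names both in one phrase but does not say that they are pooled.

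**Conclusion.** The point holds as a bias in one stated measure. Level 3 timing is conditioned on responding and averages over two kinds of cue. It is pushed towards slower if training raises responding to implicit cues and these are answered more slowly. Under the assumed rates the shift is about 85 ms at a 600 ms gap, enough to reverse a 5% speed gain and cancel a 10% gain. At a 200 ms gap it is about 28 ms, which shrinks a 5% gain without reversing it.

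A reader might infer that Level 3 will show harm when training works. The documents do not support that: they give no latencies or response rates, and the count moves the right way if the cues are the same at both visits. This should be fixed. It is not critical to the trial, because it concerns one component of the third outcome level in a self-described pilot.

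**What to change.** Revise Level 3 of the Statistical Plan, and align the Social Interaction Task section with it:

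- State the number of explicit and implicit cues and deliver the same set at both visits, or divide by cues delivered.
- Score each delivered cue as followed or not, and compare the proportion by cue type, group and visit. A mixed logistic model is one option; a simple per-participant proportion is acceptable at 20 per group.
- Analyse latency from cue onset by cue type, with non-responses censored at a prespecified window (time-to-event model or restricted mean time), in place of a mean over responses only.
- Report orienting and disengaging separately.
- Say how the proportion followed and the latency will be read together if they disagree.

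The cost is somewhat more coding and analysis work on recordings already planned, and a window that must be chosen in advance. Cue onset appears recoverable from the planned speech, gaze and video annotation, but the plan does not expressly promise it and should name it as a coded item.
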